8.2 Allowed Medications

Medications, other than those that are prohibited (Section 8.1), such as antihistamines, leukotriene antagonists, sodium cromolyn, inhaled corticosteroids, nasal corticosteroids, PPI, and/or diet therapy are allowed during the study, and unless required due to unforeseen medical necessity, doses and/or dietary modifications are to remain stable. Systemic or swallowed corticosteroids with a dose of ≤ 10 mg/day of prednisone or equivalent are acceptable, as long as the dose remains stable throughout screening and during the study. All medication use will be documented in the eCRF.

Allakos allows all types and formulations of vaccines (including live attenuated vaccines) that are authorized by the FDA (or other applicable regulatory authority) for the prevention of COVID-19. These may be administered before, during, or after the study, but should not be administered within 7 days prior to or within 7 days after the administration of study drug (so the relationship of temporally-associated AE may be more easily assessed). Any vaccine for COVID-19 that is administered during the study collection period for concomitant medications will be recorded in the CRF. Additionally, any AE occurring during the study AE collection period will be recorded in the CRF.

There is no reason to believe there is any increased risk to a subject who receives both AK002 and a vaccine for the prevention of COVID-19. In addition, there is no reason to believe AK002 negatively impacts the efficacy of a vaccine for COVID-19. Allakos will continue to monitor subject safety on an ongoing basis, paying special attention to any subject who receives the vaccine.

9. Study Treatment

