## 9.2 Appendix 2: Intercurrent Events

- A. Use of any of the following prohibited medications during the course of the study as described:
- 1) Immunosuppressive or immunomodulatory drugs (e.g., IL-5 modulators, i.e., benralizumab, reslizumab, mepolizumab; IL-4 and IL-13 antagonists, i.e., dupilumab; calcineurin inhibitors, i.e., cyclosporin, tacrolimus; mTOR inhibitors, i.e., sirolimus, everolimus; anti-metabolites, i.e., azathioprine, methotrexate, 6-mercaptopurine, leflunomide, mycophenolate mofetil; alkylating agents, i.e., cyclophosphamide; TNF inhibitors, i.e., infliximab, adalimumab; anti-IgE antibodies, i.e., omalizumab; and eosinophil depleting drugs, i.e., pramipexole).
    - a) Use at any point during the study.
  - 2) Glucocorticoids
    - a) Initiation of any course of treatment or single use of systemic or swallowed corticosteroids at a dose of  $>10$  mg/day of prednisone or equivalent starting at Week 21 and through the end of Week 24. This does not include use of corticosteroids given as pre-infusion prophylaxis or treatment of IRR.
- B. Use of restricted medications outside the protocol-defined specifications
- 1) Glucocorticoids
    - a) Discontinuation of a previously stable dose of systemic or swallowed corticosteroids ( $\leq 10$  mg/day of prednisone or equivalent) after the screening period.
    - b) Initiation of systemic or swallowed corticosteroids ( $\leq 10$  mg/day of prednisone or equivalent) following the screening period and continuing to at least Study Week 21 (within 2 weeks of efficacy assessment at Weeks 23 and 24).
  - 2) Proton Pump Inhibitors
    - a) Discontinuation of a previously stable dose of an oral PPI after the screening period and before the end of Week 24.
    - b) Initiation or increase in the dose of an oral PPI following the screening period and continuing to at least Study Week 21 (within 2 weeks of efficacy assessment at Weeks 23 and 24).

- 3) Sodium cromolyn
  - a) Discontinuation of a previously stable dose of sodium cromolyn after the screening period and before the end of Week 24.
  - b) Initiation or increase in the dose of sodium cromolyn following the screening period and continuing to at least Study Week 22 (within 1 week of efficacy assessment at Weeks 23 and 24).

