- C. Any subject requiring a therapeutic EGD (defined as dilatation or other intervention for a narrowing or stricture) that may impact subsequent assessment of the DSQ during the first qualifying EGD at the end of the screening period or at any point during the study through Study Week 24.
- D. Discontinuation of Investigational Medical Product
  - 1) Discontinuation of study agent due to
    - a) Infusion-related reaction
    - b) Subject withdrawal
    - c) Meeting study withdrawal criteria (Protocol Section 13.10)

Per protocol, subjects are required to remain on stable doses of either PPI or corticosteroids ( $\leq 10$  mg of prednisone equivalent per day) throughout the course of the study if they are on a stable dose during the screening period. Because of the potential impact of corticosteroids and PPI on both histologic assessment of tissue eosinophil levels as well as patient-reported GI symptoms, subjects must meet the entry requirements for both histology and symptom burden (DSQ) if they are on any of these medications at screening, and therefore, must remain on a stable dose throughout the study in order to meaningfully interpret any change from baseline during the evaluation phase. Conversely, subjects starting these medications due to unforeseen medical necessity following the screening period and remaining on them through a time point sufficiently close to the evaluation period to potentially impact assessment of symptoms and/or histologic assessments will be considered as ICE. For PPI and corticosteroids ( $\leq 10$  mg/day of prednisone or equivalent), a conservative washout period is estimated at 2 weeks, and therefore, continuation of a new course of therapy beyond Week 21 could be considered as a potential ICE.

Sodium cromolyn is a mast cell stabilizer and could potentially impact reported symptoms in a similar way to one of the mechanisms of action of AK002. As such, discontinuation of a previously stable dose of sodium cromolyn after the screening period and before the end of Week 24 could be considered as a potential ICE. Likewise, the initiation or increase in the dose

of sodium cromolyn following the screening period and continuing to at least Study Week 22 (within 1 week of efficacy assessment at Weeks 23 and 24) could be considered as a potential ICE. It is estimated that 1 week would be a sufficient washout period for the effects of sodium cromolyn.

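### The SAP's low-dose corticosteroid intercurrent-event rule counts starting and stopping but omits a dose increase within 10 mg/day, unlike the adjacent PPI and cromolyn rules

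*SAP*

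**What the plan says.** SAP Appendix 2 lists the medication changes that count as ICEs.

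- **Steroids at up to 10 mg/day (B.1).** Item a is "Discontinuation of a previously stable dose of systemic or swallowed corticosteroids". Item b is "Initiation of systemic or swallowed corticosteroids" after screening, continuing to at least Week 21.
- **PPI (B.2.b).** "Initiation or increase in the dose of an oral PPI following the screening period", continuing to at least Week 21.
- **Sodium cromolyn (B.3.b).** "Initiation or increase in the dose of sodium cromolyn following the screening period", continuing to at least Week 22.
- **Steroids above 10 mg/day (A.2.a).** "Initiation of any course of treatment or single use of systemic or swallowed corticosteroids at a dose of" more than 10 mg/day, "starting at Week 21 and through the end of Week 24".

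The explanatory text in the same appendix treats PPI and steroids together. Both may affect histology and symptoms, both get a two-week washout, and subjects taking either at screening "must remain on a stable dose throughout the study in order to meaningfully interpret any change from baseline". Protocol 8.2 accepts steroids at up to 10 mg/day "as long as the dose remains stable throughout screening and during the study".

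SAP 5.4.1 and 5.4.2 set to missing only the eosinophil counts and daily scores collected after an ICE. SAP 6.1.5 makes MITT the primary population.

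**The concern.** Three parallel rules sit in one list, and two of them name a dose increase. The steroid rule does not, and the SAP gives no reason for treating a steroid increase more leniently than a PPI increase. By the SAP's own reasoning an increase breaks the stability condition just as stopping does, yet only stopping is listed.

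The effect is on how data are classified. Scores recorded after an unlisted increase would be analysed as observed, so any benefit of the extra steroid would count for the arm to which the subject was randomised. The estimand question in SAP 4.2.5 concerns outcome without added medication that may affect the disease. The same change in PPI would lead to post-change DSQ being set to missing and imputed, and to the Week 24 count being handled under the ICE rule.

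**Working it through.** **1. The items side by side (SAP Appendix 2)**

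| Item | Drug | Starting | Increase | Stopping |
|---|---|---|---|---|
| A.2.a | Steroid >10 mg/day | Weeks 21–24 | not named | not named |
| B.1 | Steroid ≤10 mg/day | if continued to at least Week 21 | **not named** | yes |
| B.2 | PPI | if continued to at least Week 21 | yes | yes |
| B.3 | Cromolyn | if continued to at least Week 22 | yes | yes |

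**2. Tracing one subject.** Take a subject on a stable low dose at entry who moves mid-trial to a higher dose, still at or below 10 mg/day, and stays on it through Week 24. This is not a discontinuation (B.1.a), not an initiation (B.1.b) and not above 10 mg/day (A.2.a). No item applies. A subject who first starts low-dose steroids after screening and continues to Week 21 is already caught by B.1.b, so the gap concerns those on a dose at entry.

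**3. A neighbouring case.** If the same subject is raised above 10 mg/day before Week 21, B.1.b does not fit because of the dose, and A.2.a does not clearly fit because of its Week 21–24 window and its wording about starting a course. From Week 21 on, A.2.a may apply, if stepping up counts as starting a course.

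**4. Who could be affected.** Protocol 8.2 allows stable low-dose use, Inclusion 6 admits subjects on treatments allowed under 8.2, and B.1.a presupposes them. Against that, Exclusion 12 bars swallowed or systemic steroids within 8 weeks before screening, and the first paragraph of Protocol 8.1 prohibits them throughout participation. The documents give no count.

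**5. The plan's own figures.** SAP 3.6 gives a difference of 15 − 7.5 = 7.5, SD 15, 90% power; the two-sided 0.05 level is from SAP 5.8. The normal approximation gives n = 2 × (1.960 + 1.282)² × 15² / 7.5² = 84.1, so 85 per group. With the t distribution, power is 0.8999 at 85 and 0.903 at 86, so 86 is reproduced, and 86 / 0.86 = 100. For histology (90% vs 10%), exact Fisher power is 0.842 at 7 and 0.932 at 8 per group, so 8 is reproduced. None of these depends on the ICE wording.

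**6. Illustrative size (assumptions, not document figures).** Let 0–10% of an arm enter on a low dose, one third of them escalate, and each gain 15 DSQ points. That is the whole mean reduction planned for active treatment, so it is generous.

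- 5% entering: 5% × 1/3 = 1.7% of the arm; 1.7% × 15 = 0.25 DSQ points.
- 10% entering: 10% × 1/3 = 3.3%; 3.3% × 15 = 0.5 points.
- If all of this were a net excess on placebo, the difference would fall from 7.5 to 7.25 or 7.0, and power at 86 per group from 0.903 to 0.883 or 0.861.
- If it were a net excess on active, the difference would rise to 7.75 or 8.0. Equal escalation would largely cancel.
- Histologic response could move by at most 1.7 or 3.3 percentage points in an arm, against a planned difference of 80.

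A net placebo excess of 10% with the same gain would bring the difference to 6.0 and power to 0.742. At one third escalating, that needs 30% of the placebo arm on low-dose steroids at entry, which is hard to square with Exclusion 12.

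**The case against.** The strongest reply is that the group is close to empty. If Exclusion 12 and the first paragraph of Protocol 8.1 govern, a stable low-dose user at entry is an eligibility deviation, and the contradiction with 8.2 is the root problem. This stands as a limit on size. It does not remove the gap, because B.1.a and the SAP's rationale both plan for these subjects.

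Second, the increase may already be covered. Heading B concerns use outside protocol specifications, Protocol 4.5.4 names restricted medication, and SAP 4.2.4 names rescue medication. That reading is arguable. But Protocol 4.5.4 refers the detail to the SAP, SAP 4.2.4 refers it to Appendix 2, and the listed items there are what a programmer would apply.

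Third, if the increase is handled as rescue, Protocol 8.1 requires the EGD before rescue medication starts, and that EGD replaces Day 169. No histologic benefit is then credited. This stands, and it is why the exposure is mainly in DSQ.

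Fourth, such a subject may be a protocol deviation and leave the per-protocol set. That is possible, but the primary analysis is MITT.

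Two stronger readings are tempting. A reader might infer that steroid escalation in general escapes the ICE rules. The documents do not support that: A.2.a addresses doses above 10 mg/day in Weeks 21–24, and the rescue provisions cover other cases. A reader might also infer that the gap favours AK002. Nothing supports a direction: more escalation on placebo would shrink the estimated effect.

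**Conclusion.** The omission is real and plain in the text: an increase within 10 mg/day from a stable entry dose meets no listed ICE item, against the SAP's own stable-dose rationale. The consequence is minor. Under the stated assumptions (up to 10% entering on a low dose, one third escalating, 15 points gained each) an arm's mean DSQ change moves by at most 0.5 points and its histologic response by at most 3.3 percentage points. Both are close to zero if Exclusion 12 is applied strictly. The direction depends on which arm escalates more. This is a consistency repair worth making before unblinding. It does not show that either co-primary result would be materially biased.

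**What to change.** Before unblinding:

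1. In SAP Appendix 2 B.1.b, insert *or increase in the dose of* in place of *of* after the first word, keeping the 10 mg/day limit and the Week 21 condition, so that it parallels B.2.b and B.3.b. Extend the explanatory paragraph, which speaks only of starting, in the same way.
2. State how an increase from a stable low dose to above 10 mg/day begun before Week 21 is classified for analysis, since neither A.2.a nor B.1.b clearly covers it.
3. Reconcile Exclusion 12 and Protocol 8.1 with Protocol 8.2, Inclusion 6 and SAP B.1.a. Which clinical rule should prevail is for the sponsor to settle.

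The cost is a few words in the SAP. Protocol 11.3.1 already has dose, dates and all changes of concomitant medication recorded, so no new data are needed. The downside is that at most a few more subjects are classed as having an ICE, with their later DSQ scores imputed. No sample size changes.

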7.4 Exclusion Criteria

Subjects will be excluded from the study if they meet any of the following criteria:

- 1) Concomitant moderately or severely symptomatic EG and/or EoD*, defined as:
 - ≥ 30 eosinophils/hpf in 5 hpf in the stomach (EG) and/or ≥ 30 eosinophils/hpf in 3 hpf in the duodenum (EoD) without any other cause for eosinophilia as determined by central histology assessment of biopsies collected during the Screening EGD.

and

- EG/EoD PRO Questionnaire weekly average single symptom score of ≥ 3 during the last 2 weeks of screening for 1 of the following symptoms: abdominal pain, nausea, and/or diarrhea.
- * This exclusion criterion is only applicable to sites actively enrolling subjects in the AK002-016 study. If a site is *not* actively screening and enrolling subjects in the AK002-016 study, then this exclusion criterion is not applicable.
- 2) Causes of esophageal eosinophilia other than EoE or one the following: hypereosinophilic syndrome, eosinophilic granulomatosis with polyangiitis, or peripheral blood absolute eosinophil count >1500 eosinophils/ μL .
 - 3) History of inflammatory bowel disease, celiac disease, achalasia, and/or esophageal surgery.
 - 4) Any esophageal stricture unable to be passed with a standard diagnostic 9 mm to 10 mm upper endoscope or any critical esophageal stricture that requires dilation during screening.
 - 5) History of bleeding disorders or esophageal varices.
 - 6) History of malignancy, except carcinoma in situ, early stage prostate cancer, or non-melanoma skin cancers. However, cancers that have been in remission for more than 5 years and are considered cured can be enrolled (with the exception of breast cancer).

All history of malignancy (including diagnosis, dates, and compliance with cancer screening recommendations) must be documented and certified by the Investigator, along with the statement that in their clinical judgment the tissue eosinophilia is attributable to EGID, rather than recurrence of malignancy.

- 7) Active *Helicobacter pylori* infection (as determined by central histology staining of the biopsy collected during the Screening EGD), unless treated and confirmed to be negative prior to randomization and symptoms remain consistent.

- 8) Positive Ova and Parasite test at screening, seropositive for *Strongyloides stercoralis* at screening, and/or treatment for a clinically significant helminthic parasitic infection within 6 months of screening.

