10.2 Stratification and Randomization

To be randomized into the study, a subject must meet all inclusion criteria and no exclusion criteria. Subjects will be randomized through the IRT system.

If the subject qualifies for the study after completing all screening procedures, on the day of first infusion (Study Day 1), the site will access the IRT system in order to randomize and stratify the subject in the study and enter the current body weight for study drug dose calculation. Subjects will be stratified at randomization based on age (12–17 and ≥ 18 years) and baseline DSQ score (≤ 30 and > 30). The IRT system will randomly assign the subject to a low dose AK002 regimen (6 doses of 1 mg/kg), a high dose AK002 regimen (first dose at 1 mg/kg, subsequent 5 doses at 3 mg/kg), or placebo in a double-blind approach and will email the kit (vial) number to the study pharmacist.

Approximately 300 subjects with symptomatic EoE will be randomized 1:1:1 to receive 1 of 3 dose regimens in a double-blind fashion: 100 subjects will be randomized to the low dose regimen (1 mg/kg AK002 administered every 4 weeks for 6 doses); 100 subjects will be randomized to the high dose regimen (1 mg/kg AK002 for the first dose followed by 3 mg/kg AK002 administered every 4 weeks for the 5 subsequent doses); and 100 subjects will be randomized to placebo. A subject is considered enrolled in the study when the subject is randomized.

For subsequent infusions on Days 29, 57, 85, 113, and 141, the site will access the IRT system on the day of infusion and enter the PID as well as the subject's body weight, and the system will assign the vial(s) on the dose regimen associated with the randomization number. The study pharmacist will then receive an email detailing the kit (vial) number to prepare.

Prior to each infusion, the Investigator or designee will confirm that the PID recorded on the IV bag provided by the study pharmacist matches the subject. The subject's identification should be confirmed and documented by a second party prior to administering the infusion, whenever possible.

The assignment of treatments to AK002 or placebo will be securely retained in the IRT system until such time as designated by the Statistical Analysis Plan.

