#### **4.2.4 Intercurrent Events**

The events below are considered intercurrent events (ICE) confounding with the efficacy outcomes.

- Premature discontinuation from the study
- Use of prohibited/rescue medication
- Any therapeutic EGD (defined as dilatation or other intervention for a narrowing or stricture of the esophagus) at any point during the study through Week 24.

Further clarification and handling of ICE including prohibited/rescue medications is detailed in [Appendix 2](#).

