#### **4.2.5 Strategy for Handling Intercurrent Events**

Per the study protocol, if a prohibited medication is started during the course of the study, the subject will be withdrawn from study treatment and followed for the 12-week follow-up period. In addition, the follow-up EGD may not be performed. Thus, for analysis of the trial product estimand, tissue eosinophil values and DSQ scores will be counted as non-responders for binary variables and set to missing for continuous outcomes from the point when an ICE occurs. An appropriate method for handling missing data through statistical modeling (e.g., multiple imputation [MI]) will be used (Sections [5.4.1](#), [5.4.2](#), and [6.11](#)). The estimand will provide an answer to the question that is crucial to individual subjects:

“If I take this study drug as part of my treatment regimen, without adding any further medications or the use of therapeutic endoscopic interventions that may impact the underlying disease or exit the study prematurely, what improvements in histology and PRO symptoms might be anticipated after 24 weeks?”

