### 5.4 Handling of Dropouts, Missing Data, and Data Discrepancies

#### 5.4.1 Missing Tissue Eosinophil Count at Week 24

Eosinophil counts will be set to missing if they are collected after subjects have experienced ICE. Subject with missing Week 24 tissue eosinophil count for any reason will be imputed with the eosinophil count collected from the post-baseline unscheduled visit prior to missing. If no eosinophil count is collected post-baseline, the subject will be considered treatment failure for tissue eosinophil response.

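### SAP Appendix 2 counts a therapeutic endoscopy at screening, before randomisation, as an intercurrent event, so an affected subject's on-treatment histology and DSQ are discarded

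*SAP*

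**What the plan says.** Item C of SAP Appendix 2 (section 9.2) makes a therapeutic EGD, meaning a dilation or similar procedure for a stricture, an ICE if it is one "that may impact subsequent assessment of the DSQ". Two time frames are joined by an or: the procedure may take place "during the first qualifying EGD at the end of the screening period", or later in the study up to Week 24.

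The main-text lists are narrower. SAP 4.2.4 counts a therapeutic EGD "at any point during the study through Week 24". Protocol 4.5.4 sets the same limit. Neither names the screening EGD.

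Protocol 10.2 places randomisation after all screening procedures: "on the day of first infusion (Study Day 1), the site will access the IRT system in order to randomize".

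The handling rules are these:
- SAP 4.2.5: outcomes are "counted as non-responders for binary variables and set to missing for continuous outcomes from the point when an ICE occurs".
- SAP 5.4.1: "Eosinophil counts will be set to missing if they are collected after subjects have experienced ICE". A missing Week 24 count is replaced by an earlier unscheduled post-baseline count if there is one. Otherwise: "If no eosinophil count is collected post-baseline, the subject will be considered treatment failure for tissue eosinophil response".
- SAP 5.4.2: daily PRO scores after an ICE become missing, and missing DSQ is multiply imputed within each treatment group.

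Protocol 7.4, criterion 4, excludes strictures that a standard endoscope cannot pass and "any critical esophageal stricture that requires dilation during screening".

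**The concern.** A procedure done at the screening EGD precedes both randomisation and the first dose. For the comparison of arms it is a baseline characteristic, and randomisation balances it in expectation. It says nothing about what happened on treatment.

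The ICE rules discard everything from the event onward. When the event comes before Day 1, that means the whole treatment period. A subject on active drug with no eosinophils at Week 24 would still be scored a failure on the first co-primary endpoint, on the two other histologic thresholds (at most 1 and fewer than 15 per hpf) and on treatment response. Item C justifies itself by the effect of the procedure on the DSQ, yet the rule also voids the biopsy.

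The estimand question in SAP 4.2.5 asks about taking study drug without adding further medication or endoscopic intervention. A procedure completed before treatment is not an addition to it. SAP 4.2.1 defines the target population by the eligibility criteria, which a subject dilated for a non-critical stricture can meet.

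**Working it through.** **Tracing the rules for one subject.** Take a subject dilated at the screening EGD for a non-critical stricture, where the procedure may affect the DSQ. The subject is randomised and dosed, and so belongs to the MITT population, which is primary under SAP 6.1.5.

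1. The ICE date is before Day 1.
2. Every post-baseline eosinophil count falls after the ICE and is set to missing. That includes any unscheduled count, so nothing can be carried forward and the subject is a histologic failure.
3. The subject is also a non-responder on the DSQ responder endpoints (SAP 4.2.5).
4. Weeks 1–2 to Weeks 23–24 make 24 / 2 = 12 biweekly DSQ scores. All 12 are missing and are drawn from the own-arm model, using the subject's baseline data only.
5. Baseline DSQ comes from the 14 days before the first dose (SAP Table 2), and the screening EGD may be up to 35 days before Day 1. The sentence in SAP 5.4.2 that deletes scores after an ICE has no start date, although the section title refers to Weeks 23–24. Read literally, it removes part of the baseline DSQ if the EGD falls inside the 14 days, and all of it if the EGD is earlier.

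No step depends on treatment arm.

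**The plan's own figures (SAP 3.6).**
- DSQ: difference 15 − 7.5 = 7.5, SD 15, two-sided 0.05. Power = Φ(7.5 / (15 × √(2/n)) − 1.96). At n = 86 this is Φ(3.279 − 1.960) = 90.6%; with the t distribution it is 90.3%. The stated 86 is reproduced.
- Histology, 90% against 10%: exact Fisher power is 84.2% at 7 per arm and 93.2% at 8. The stated 8 is reproduced.
- Dropout: 86 / (1 − 0.14) = 100 per arm.

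**Size of the effect.** The documents give no rate of screening dilation, so let a share f of each arm be affected. Three assumptions are made: affected subjects would otherwise respond like the rest, f is the same in each arm, and the DSQ information comes only from subjects with observed data.

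- Histologic difference = (1 − f) × (90 − 10) points.
- DSQ power uses n = 100(1 − f), or n = 86(1 − f) if the planned dropout also occurs.

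| Assumed f | Histologic difference (points) | DSQ power, 100(1 − f) per arm | DSQ power, 86(1 − f) per arm |
|---|---|---|---|
| 0 | 80 | 94.2% | 90.6% |
| 1% | 79.2 | 94.0% | 90.4% |
| 5% | 76 | 93.1% | 89.2% |
| 10% | 72 | 91.8% | 87.5% |

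As an example, at f = 5% and n = 95: Φ(7.5 / (15 × √(2/95)) − 1.96) = Φ(3.446 − 1.960) = 93.1%. Histology power at 100 per arm stays at about 100% throughout; at f = 10% the rates are 81% and 9%.

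**The case against.** **Few subjects may be affected.** Criterion 4 removes the severe strictures, and the protocol describes the screening EGD as grading and biopsy, with no provision for dilation. Item C also applies only where the procedure may affect the DSQ, so not every screening dilation is an ICE. All of this stands and limits the reach. It does not close the gap: criterion 4 requires a stricture to be critical or impassable, item C does not, and nobody is named to judge whether the DSQ may be affected. If no subject qualifies, the clause does nothing and removing it loses nothing.

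**The clause has a purpose.** If the dilation falls within the 14-day baseline window, the baseline DSQ mixes days before and after it, and part of the later change may reflect the procedure. This stands as a cost of removing the clause. It adds some noise to DSQ change, balanced across arms in expectation. It is no reason to discard the biopsy.

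**The main-text lists could be read to include screening,** since they give no starting point. But Appendix 2 sets the screening EGD beside the rest of the study as a separate item, so the sections at least need reconciling.

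Two stronger readings are tempting. A reader might infer that the rule favours one arm; the documents do not support this, because the event precedes randomisation and the handling is the same in every arm. A reader might also infer that these subjects drop out of both co-primary analyses. They do not: they stay in the MITT population, as failures for histology and as own-arm imputed values for DSQ. What is lost is their observed outcomes.

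**Conclusion.** The point holds as a minor one. Item C turns a pre-randomisation procedure into an ICE, which the main-text lists do not name, and the handling rules then give a wrong result on the first co-primary endpoint for any such subject with a histologic response at Week 24. The harm is dilution and lost information.

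The number of subjects is unknown and probably small. Over the assumed range of 1% to 10%, the histologic conclusion is not at risk. DSQ power falls by 0.2 to 2.4 points at 100 per arm, or by 0.2 to 3.1 points with 14% dropout. These figures rest on the plan's own effect sizes and on the assumptions stated with the calculation.

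**What to change.** In item C, delete the words "during the first qualifying EGD at the end of the screening period" together with the conjunction that follows, and state that only a therapeutic EGD after the first dose and through Week 24 is an ICE. Put the same starting point in SAP 4.2.4, so that the appendix and the main text agree.

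Keep the observed histology and DSQ of subjects dilated at screening in the primary analysis. List these subjects by arm and, if there are any, add a DSQ sensitivity analysis without them. State in SAP 5.4.2 that the deletion of scores after an ICE does not reach the baseline DSQ.

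The cost is a short SAP amendment before database lock, one listing and at most one extra DSQ analysis. The remaining downside is the noise from a dilation inside the baseline window, which the sensitivity analysis would show. Handling screening dilation through eligibility instead would need a protocol amendment, not a SAP edit, and is not needed for this correction.
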